5.4 Removal of Subjects from Therapy or Assessment

5.4.1 Discontinuation of Individual Subjects

Each subject has the right to withdraw from the study and/or study drug treatment at any time. In addition, the Investigator may discontinue a subject from study drug treatment at any time if the investigator considers it necessary for any reason including:

- The investigator believes it is in the best interest of the subject;

- Subject's response to therapy is unsatisfactory, as evidenced by progression of disease while on study drug.
- The subject requires other cancer treatment (e.g., radiotherapy, cancer-related surgery as a result of tumor progression, alternate anti-neoplastic agents) during the study period
- unacceptable toxicity
- The subject becomes pregnant while on the study
- drug/protocol non-compliance

The investigator will inform AbbVie prior to discontinuing a subject from the study by contacting the Clinical Team Leader as identified in Section 7.0. All subjects will be included for analysis of safety data. Subjects who withdraw from the study will not be replaced unless they are not evaluable.

Subjects will continue to be followed for unresolved AEs and survival information for any subject who has not experienced PD at the time of venetoclax discontinuation.

Final Visit

Upon study drug discontinuation and/or upon discontinuation from the study, the reason(s) for discontinuation will be recorded in electronic case report forms (eCRFs) and a final visit will be performed. The final visit procedures as listed in [Appendix D](#) should be performed as soon as possible after discontinuation from study drug.

30-Day Safety Follow-Up Visit

A 30-Day Safety Follow-up Visit should be performed approximately 30 days (\pm 3 days) following the last dose of venetoclax. The 30 day safety follow up procedures listed in [Appendix D](#) should be performed.

Post Treatment and Survival Follow-Up Calls

For subjects who discontinue venetoclax therapy, but do not discontinue the study (), post-treatment follow-up calls will be performed every 6 months (\pm 7 days) for survival

information (i.e., disease progression, the date and cause of death, post-treatment cancer therapies, etc.) and will be collected via telephone calls for a period of 2 years and recorded in the eCRFs.

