6.1.3 Adverse Events Expected Due to Study-Related Endpoints

6.1.3.1 Deaths

For this protocol, overall survival is an efficacy endpoint. Deaths that occur during the protocol-specified adverse event reporting period (Section 6.1.5) that are attributed by the investigator solely to progression of CLL should be recorded ONLY on the Study Completion eCRF. All other on-study deaths, regardless of relationship to study drug, must be recorded on the Adverse Event eCRF and immediately reported to the Sponsor (Section 6.1.5). Death should be considered an outcome and not a distinct event. The event or condition that caused or contributed to the fatal outcome should be recorded as the single medical concept on the Adverse Event eCRF. Generally, only one such event should be reported. The term "sudden death" should be used only for the occurrence of an abrupt and unexpected death due to presumed cardiac causes in a subject with or without preexisting heart disease, within 1 hour after the onset of acute symptoms or, in the case of an unwitnessed death, within 24 hours after the subject was last seen alive and stable. If the cause of death is unknown and cannot be ascertained at the time of reporting, "unexplained death" should be recorded on the Adverse Event eCRF. If the cause of

death later becomes available (e.g., after autopsy), "unexplained death" should be replaced by the established cause of death. During survival follow-up, deaths attributed to progression of CLL should be recorded only on the Survival eCRF.

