Time to progression (TTP) will be defined as the number of days from the date of first dose or enrollment if not dosed to the date of earliest disease progression. All disease progression will be included regardless whether the event occurred while the subject was taking the study drug or had previously discontinued the study drug. If the subject does not experience disease progression, then the data will be censored at the date of last available disease assessment. Data for subjects who receive non-protocol, CLL therapy prior to disease progression will be censored at the last disease assessment prior to receiving non-protocol therapy. Data for subjects without any disease assessments performed after the baseline visit will be censored at the time of enrollment plus 1 day. TTP will be analyzed by Kaplan-Meier methodology using data for all subjects enrolled. Median time TTP will be calculated and 95% confidence interval for median time TTP will be presented.

Progression-free survival (PFS) will be defined as the number of days from the date of first dose to the date of earliest disease progression or death. All disease progression will be included regardless whether the event occurred while the subject was taking the study drug or had previously discontinued the study drug. If the subject does not experience disease progression or death, then the data will be censored at the date of last disease

assessment. Data for subjects who receive non-protocol, CLL therapy prior to disease progression will be censored at the last disease assessment prior to receiving non-protocol therapy. Data for subjects without any disease assessments performed after the baseline visit will be censored at the time of enrollment plus 1 day. PFS will be analyzed by Kaplan-Meier methodology using data for all subjects enrolled. Median time PFS will be calculated and 95% confidence interval for median time PFS will be presented.

Overall survival (OS) will be defined as number of days from the date of first dose to the date of death for all dosed subjects. For subjects who did not die, their data will be censored at the date of last study visit or the last known date to be alive, whichever is later. OS will be analyzed by Kaplan-Meier methodology using data from all enrolled subjects. Median time survival will be estimated and 95% confidence interval for the median time survival will be presented.

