Overall survival (time to death) for a given subject will be defined as the number of days from the date the subject started venetoclax to the date of the subject's death (i.e., $OS = \text{death/censoring date} - \text{first dose date} + 1 \text{ day}$). All events of death will be included, regardless of whether the event occurred while the subject was still taking venetoclax, or after the subject discontinued venetoclax. If a subject has not died, then the data will be censored at the date of the last study visit, the last contact date, the date the subject was last known to be alive, or at the cut-off date for the interim analysis if the subject has a death that is after the cut-off date. The date of the last study visit will be determined by selecting the last available date of the following study procedures for a subject: tumor assessment, clinical disease progression, physical examination, vital signs assessment, clinical laboratory collection, study drug, adverse event and concomitant medication assessment, performance status, quality of life evaluation, survival form, and drug and study completion form. The distribution of the time to death will be estimated using Kaplan-Meier methodology. Median survival time and the corresponding 95% confidence interval will be estimated.

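### The OS censoring rule can take a study completion form date later than the last evidence that a lost subject was alive

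*SAP*

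**What the plan says.** SAP 10.1.2 (Overall Survival) states that a subject who has not died is "censored at the date of the last study visit, the last contact date, the date the subject was last known to be alive"; the cutoff is a further alternative. It does not say which of these dates governs. It then defines one of them: "The date of the last study visit will be determined by selecting the last available date of the following study procedures for a subject". Most of the list consists of assessments made on the subject, such as tumour assessment, examination, vital signs and laboratory collection. It closes with "performance status, quality of life evaluation, survival form, and drug and study completion form". The date field to be read from the two forms is not named.

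Protocol 8.1.2.2 does have a selection rule, which for survivors reads: "their data will be censored at the date of last study visit or the last known date to be alive, whichever is later".

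Three other places bear on the point:

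- **Protocol 5.4.1** sets the spacing of survival contacts after treatment: "post-treatment follow-up calls will be performed every 6 months", for 2 years. It also covers leaving the study: "Upon study drug discontinuation and/or upon discontinuation from the study, the reason(s) for discontinuation will be recorded in electronic case report forms".
- **Protocol 6.1.3.1** uses the study completion form as a status record. Deaths in the adverse event reporting period that are attributed solely to CLL progression "should be recorded ONLY on the Study Completion eCRF".
- **SAP 6.4** censors subjects whose last-known-alive date is missing at the interim data cutoff.

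**The concern.** A censoring date for OS should be a date on which the subject was known to be alive. Up to that date a death would have been seen; after it, a death could not be. The study completion form for a subject declared lost is, by its nature, filled in after contact has ended. If its date is later than the last contact, the maximum-date rule in SAP 10.1.2 picks it up, and the later-of rule in the protocol keeps it.

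The subject then stays in the risk set for a period in which no event can be recorded. Every death among other subjects in that period is divided by a risk set that is too large, so each Kaplan-Meier step is too small or unchanged. The error has one direction. In a single-arm study no comparator shares it.

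**Working it through.** **1. The plan's own figure.** There is none for OS: no event count, rate, power or loss rate. The sample size of 177 rests on the GHS/QoL scale and does not use OS. The sizes below are therefore illustrations under assumed rates.

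**2. When does the form entry matter?** SAP 10.1.2 already lists the last contact date and the last-known-alive date separately. If a form carries a true contact date, including the form adds nothing to them. It changes the result only when its date is later than any documented evidence of life. Restricting the list therefore discards no valid follow-up.

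**3. Size.** Assumptions, none from the documents: exponential death at monthly rate h, exponential loss at monthly rate c, and lost subjects censored g months after last contact. At time t the risk set holds the subjects truly under observation plus those lost during the previous g months. The apparent hazard is

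h / [1 + (c/(h+c)) × (exp((h+c) × min(t, g)) − 1)],

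which for small rates and t > g is about h/(1 + c × g).

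Worked case: true 24-month OS 80%, loss 5% per year, g = 6.

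- h = −ln(0.80)/24 = 0.009298; c = −ln(0.95)/12 = 0.004274; h + c = 0.013572.
- After month 6: (0.004274/0.013572) × (exp(0.08143) − 1) = 0.3149 × 0.08484 = 0.0267, so the hazard is multiplied by 1/1.0267 = 0.9740. Over months 0–6 the average multiplier is 0.9871.
- Cumulative hazard at 24 months = 0.009298 × (6 × 0.9871 + 18 × 0.9740) = 0.2181, and exp(−0.2181) = 80.4%.
- Overstatement: 0.4 points.

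A Kaplan-Meier simulation of 1,000,000 subjects per scenario, on the same assumptions, agrees: 80.03% when censoring at last contact and 80.44% with the 6-month lag. The full range of simulated 24-month OS (%) is:

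| True 24-month OS | Loss per year | No lag | 6-month lag | 12-month lag | Lost subjects censored at a 36-month cutoff |
|---|---|---|---|---|---|
| 90% | 2% | 89.96 | 90.05 | 90.11 | 90.16 |
| 90% | 10% | 89.95 | 90.39 | 90.69 | 90.93 |
| 80% | 5% | 80.03 | 80.44 | 80.74 | 80.99 |
| 80% | 10% | 80.05 | 80.87 | 81.46 | 81.93 |
| 60% | 2% | 59.93 | 60.22 | 60.45 | 60.66 |
| 60% | 10% | 59.91 | 61.39 | 62.54 | 63.53 |

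A 6-month lag (one missed call) adds about 0.1 (90.05 − 89.96) to 1.5 points (61.39 − 59.91). A 12-month lag adds about 0.2 to 2.6. The last column shows what the SAP 6.4 rule does if it is applied to every lost subject: about 0.2 to 3.6.

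**4. Horizon.** The last cutoff in SAP Table 1, and the only one that includes efficacy data, is 30 Apr 2018. The original protocol is dated 04 May 2016, 726 days earlier, so no subject has a full 24 months at that cutoff. At 12 months the same formula gives about 0.04 to 0.8 points for a 6-month lag. The 24-month figures apply to the later data that Protocol 8.1.3 says will be collected.

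**5. The planned summary.** The SAP plans the Kaplan-Meier distribution and the median, not a landmark rate. The true median is 24 × ln 2 / (−ln S24), where S24 is the true 24-month OS: about 158, 75 and 33 months for S24 of 90%, 80% and 60%. None is reached by 726 days. Only the last falls within 4 years (2 of treatment plus 2 of calls). In its worst case (10% loss, 6-month lag) the median moves from 32.6 to 34.3 months.

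**The case against.** The strongest reply is that the documents never define the date fields. The SAP does not say that a form's completion date is used; the date taken could be the call date or the status date. On three points this reply stands.

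- **Certainty.** A reader might infer that every lost subject is credited with survival up to a paperwork date. The text does not support that. SAP 10.1.2 states no rule among its censoring dates, and the later-of rule is in the protocol, which does not define the last visit by forms. The over-credit is permitted, not required.
- **The survival form.** A reader might infer that listing it is an error. It is not: survival information is collected by telephone, and a form dated from a successful call is good evidence of life. Nothing says that sites complete it after an unanswered call. Likewise, Protocol 5.4.1 pairs the recording of discontinuation with a final visit, so many completion forms will coincide with a real contact. The exposed case is the completion form of a subject declared lost.
- **Size at the listed cutoff.** A reader might carry the effect to 3-year OS, or to form dates running to the end of the 2-year call period. Neither can occur within the 726 days available at the last Table 1 cutoff.

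What the reply does not remove is the gap itself. A maximum-date rule that includes status forms, with no evidence-of-life condition, has no useful function beyond the contact and last-known-alive dates already listed.

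**Conclusion.** The point holds as a gap in the SAP wording, of minor importance. A subject lost to follow-up can be censored for OS at a study completion form date later than the last evidence of life, and the resulting bias in the Kaplan-Meier curve is zero or upward. With assumed 24-month OS of 60–90% and loss of 2–10% per year, a 6-month lag is worth about 0.1–1.5 percentage points at 24 months. It is zero if form dates are confirmed-alive dates, and SAP 10.2 limits it to data before the cutoff. The median is unlikely to change, except in later data if survival is near the low end of the assumed range. OS is a secondary, descriptive endpoint, and the primary quality-of-life result is unaffected. The documents do not show that the bias will occur, only that the rule allows it.

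**What to change.** In SAP 10.1.2, replace the list-based rule with one sentence: censor OS at the latest date on which the subject is documented to be alive, on or before the data cutoff. Then specify the sources:

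- From the survival form, take the contact or last-known-alive date, not the date the form was completed.
- Use the study completion form date only where it records contact with the subject, and not where the reason is loss to follow-up.
- Align SAP 6.4, which biases OS in the same direction: a missing last-known-alive date should be replaced by the latest documented evidence of life, not by the data cutoff.

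The cost is a short SAP edit and a small change to the program that derives the censoring date. No new data collection is proposed. Follow-up for lost subjects becomes slightly shorter.

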10.2 Quality of Life and Efficacy Analyses

Data collected at any point prior to the specified interim cutoff date during the study will be used in the analyses, unless otherwise specified. The population of these analyses is defined in Subsection [5.1.1](#).

10.2.1 Primary Endpoint Analysis

The primary endpoint will be assessed by the GHS/QoL subscale of the EORTC QLQ-C30. Summary stats will be on mean change. The endpoint (at subject level) will be mean change from baseline to Week 48. Scores will be calculated based on the scoring manual. Mean score for baseline visit and post-baseline visit (Week 4, Week 12, Week 24, Week 36, Week 48, Week 60, Week 72, Week 84, Week 96, and Week 108/Final visit) will be reported with standard deviation (SD). The 95% confidence interval for mean change additionally will be provided for each post-baseline versus baseline.

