Study visits will be reduced to a monthly frequency at Week 8, and at Week 48, they will be reduced to every 3 months until the end of study treatment (Week 108). In countries where venetoclax is not commercially available, subjects who continue to derive benefit after 2 years of treatment may be able to extend their treatment for up to 2 additional years. Quality of life assessments will be performed within 72 hours prior to the first dose of venetoclax, and at Week 4, Week 8, Week 12, Week 24, Week 36, and Week 48, then every 12 weeks thereafter until the end of study treatment (Week 108). A Disease Assessment for clinical response by physical exam and hematologic assessments will be performed at Week 24, Week 36 and Week 48. To confirm the response, a CT scan will be performed at Week 48 on all subjects. When confirming a CR or CRi status per 2008 Modified International Workshop for Chronic Lymphocytic Leukemia National Cancer Institute Working Group (IWCLL-NCI-WG) criteria a bone marrow (BM) biopsy and aspirate should also be performed. After treatment discontinuation, a final visit will be performed. Subjects will be followed for disease progression (if progression has not already occurred) and survival. Post-treatment follow up calls will be performed every 6 months until discontinuation from the study. Survival information (i.e., the date and cause of death, post-treatment cancer therapies, date of progression etc.) will be collected. This period will continue for 2 years following discontinuation of venetoclax.

The Data Monitoring Committee (DMC) will review safety data intermittently according to the DMC charter. Subsequent reviews may be conducted based on recommendations from the DMC or requests from the Sponsor. Details of the DMC review will be presented in the DMC charter.

Diagnosis and Main Criteria for Inclusion/Exclusion:

Main Inclusion:

A subject will be eligible for study participation if he/she meets all of the following criteria:

1. Age \geq 18 years.
2. Eastern Cooperative Oncology Group (ECOG) performance score of \leq 2.
3. Subject has relapsed/refractory disease (received at least one prior therapy).
4. Diagnosis of CLL that meets published 2008 Modified IWCLL NCI-WG guidelines and:
 - has an indication for treatment according to the 2008 Modified IWCLL NCI-WG criteria

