5.3.2.1 Primary Variable

The primary endpoint will be based on the mean change from baseline to Week 48 on the GHS/QoL subscale of the EORTC QLQ-C30. Subjects will complete the EORTC QLQ-C30, along with other PRO measures, at baseline (within 72 hours prior to the first dose of venetoclax), Week 4, Week 8, Week 12, Week 24, Week 36, and Week 48, then every 12 weeks thereafter until the end of treatment (Week 108). The GHS/QoL subscale will be calculated as per the EORTC scoring manual, and summarized (mean, std dev, median) at each visit.

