6.3 Definition of Analysis Windows

For visit wise analyses including quality of life and safety analyses, the time windows specified in [Table 2](#) and [Table 3](#), describe how the data will be assigned to protocol specified visits. Analysis time windows will be constructed using the following algorithm:

- Determine the nominal study Rx day for each scheduled visit.
- Determine the time window around a specific nominal study Rx day as in [Table 2](#).
- If more than one assessment is included in a time window the most conservative value (i.e., the smallest score) should be used for the analysis of quality of life measures. A sensitivity analysis should be performed based on considering the most favorable (i.e., the largest value) assessment of the quality of life measures. Except the quality of life measures, if there are two observations with equal distance to the nominal day, the latest one will be used in analyses.

Table 2. Time Windows for Quality of Life Measures

Scheduled Visit	Nominal Day	Time Window (study Rx day range)
Baseline (Week 1 Day -1 or Week 1 Day 1)	≤ 1	See the baseline definition (Section 6.0)
Week 4 Day 1	22	2 to 43
Week 8 Day 1	50	44 to 71
Week 12 Day 1	75	72 to 153
Week 24 Day 1	162	154 to 237
Week 36 Day 1	246	238 to 321
Week 48 Day 1	330	322 to 405
Week 60 Day 1	414	406 to 489
Week 72 Day 1	498	490 to 573
Week 84 Day 1	582	574 to 657
Week 96 Day 1	666	658 to 743
Week 108 Day 1	750	742 to 825
Final Observation	Last non-missing value within 30 days of last dose of Venetoclax	

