10.1.1 Definitions for Quality of Life Assessments

EORTC QLQ-C30

Quality of life and symptoms will be assessed with the European Organization for Research and Treatment of Cancer (EORTC) Quality of Life Questionnaire Core 30 (EORTC-QLQ-C30) version 3¹. The QLQ-C30 is a 30-item subject self-report questionnaire composed of both multi-item and single scales, including five functional scales (physical, role, emotional, social, and cognitive), three symptom scales (fatigue, nausea and vomiting, and pain), a global health status/quality of life (GHS/QoL) scale, and six single items (dyspnea, insomnia, appetite loss, constipation, diarrhea, and financial difficulties). Subjects rate items on a four-point scale, with 1 as "not at all" and 4 as "very much." The EORTC QLQ-C30 was developed and validated for use in a cancer subject population, and its reliability and validity is highly consistent across different language cultural groups. A change of 5 – 10 points is considered a small change, and the lower bound (5) is being used to define the minimum important difference (MID). A change of 10 – 20 points is considered a moderate change.

The EORTC-QLQ-C30 domains (global health status/quality of life, physical, role, emotional, social, cognitive, fatigue, nausea and vomiting, pain, dyspnoea, insomnia, appetite loss, constipation, diarrhea, and financial difficulties) will be summarized (mean, standard deviation, and median) at each assessment. In addition the mean change in each of these values (visit-level assessment versus baseline) will be calculated to identify any statistically significant differences. The ninety-five percent (95%) confidence interval of the mean change will be constructed based on (a) without model assumption and (b) with model assumption. A linear model will be used for the analysis of repeated measures where the covariance pattern will be assumed as compound symmetry (CS).

EORTC QLQ-CLL16

The EORTC QLQ-CLL16 was designed specifically for subjects with stage 0 to stage 4 CLL². It is comprised of sixteen questions that address five domains of HRQoL important in CLL. There are three multi-item scales assessing Fatigue (2 items), Disease

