10.2.2 Secondary Efficacy Analyses

ORR and CR will be assessed as the proportion of subjects with an overall response based on the IWCLL NCI-WG criteria. The 95% confidence interval based on the Clopper-Pearson exact method for binomial distribution will be constructed for the calculated ORR and CR rates.

DOR, TTP, PFS, and OS will be analyzed by Kaplan-Meier methodology using data for all subjects defined in Section 5.1.1. Median time of each endpoint will be calculated and 95% confidence interval for median time of each endpoint will be presented.

Secondary quality of life endpoints will include all multi-item scales and single-item scales from the EORTC QLQ-C30, EORTC QLQ-CLL16, and EQ-5D-5L. Scores will be calculated based on the scoring manual for each instrument. The mean change score from baseline to post-baseline (Week 4, Week 12, Week 24, Week 36, Week 48, Week 60, Week 72, Week 84, Week 96, and Week 108/Final visit) will be summarized with the 95% confidence interval. Mean score with SD of baseline and each post-baseline visit also will be presented.

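### The by-visit quality-of-life lists in SAP 10.2.1 and 10.2.2 leave out Week 8 and combine Week 108 with the Final visit, contradicting SAP 10.1.1, SAP Table 2 and Protocol 5.3.2.1

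*SAP*

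**What the plan says.** **Collection.** The protocol synopsis schedules the questionnaires before the first dose and then at "Week 4, Week 8, Week 12, Week 24, Week 36, and Week 48, then every 12 weeks thereafter" until Week 108. The Appendix D schedule marks them at Week 8 Day 1. Protocol 5.3.2.1 says that the GHS/QoL subscale is to be scored "and summarized (mean, std dev, median) at each visit".

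**SAP visit lists.** SAP 10.2.1 lists the post-baseline visits as "Week 4, Week 12, Week 24, Week 36, Week 48, Week 60, Week 72, Week 84, Week 96, and Week 108/Final visit". SAP 10.2.2 uses the same visits for the other scales: "The mean change score from baseline to post-baseline (Week 4, Week 12, Week 24, Week 36, Week 48, Week 60" and onward to the same combined last entry.

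**Other SAP text.** SAP 10.1.1 says that the QLQ-C30 domains, with GHS/QoL named first, "will be summarized (mean, standard deviation, and median) at each assessment", and that "the mean change in each of these values (visit-level assessment versus baseline) will be calculated", with a 95% confidence interval. It has matching text for QLQ-CLL16 and EQ-5D-5L. SAP 10.2.2 ends with "Mean score with SD of baseline and each post-baseline visit also will be presented".

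**Windows.** SAP Table 2 gives Week 8 its own row (nominal day 50, Rx days 44 to 71). It has one row for Week 108 Day 1 (Rx days 742 to 825) and a separate row for Final Observation, defined as "Last non-missing value within 30 days of last dose of Venetoclax". SAP 6.2 treats Final Observation and Final Visit as the same thing.

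**The concern.** The SAP is meant to guide programming, and it gives two incompatible instructions for the same tables without saying which governs. A programmer who follows the explicit list in 10.2.1 or 10.2.2 produces no Week 8 row. One who follows 10.1.1 and Table 2 produces it.

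The visit in question is informative. Titration reaches 400 mg at Week 5, so Week 4 Day 1 (day 22) precedes the target dose and Week 8 Day 1 (day 50) is the first scheduled assessment at it. Without Week 8, the first such point is the Week 12 row, whose window runs from day 72 to day 153.

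The combined last row has a similar problem. Protocol 5.3.1.1 performs the Final Visit at treatment discontinuation, and Appendix D schedules questionnaires at it, so early discontinuers can have a Final Visit value. If those values enter a row labelled Week 108, its mean describes neither subjects at Week 108 nor all subjects at end of treatment.

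**Working it through.** **1. The plan's own sample size, to see whether it is touched.** Inputs from SAP 4.3: difference 5, SD 20.5, one-sided alpha 0.025, power 90%.

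n = [SD × (z₀.₉₇₅ + z₀.₉₀) / difference]² = [20.5 × (1.960 + 1.282) / 5]² = 176.63, rounded up to 177.

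This agrees with the plan. It concerns Week 48 only, so neither the missing Week 8 nor the combined last row enters it.

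**2. Visit count.**

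| Source | Post-baseline visits | Count |
|---|---|---|
| Protocol schedule | Weeks 4, 8, 12, 24, 36, 48, 60, 72, 84, 96, 108 | 11 |
| SAP 10.2.1 and 10.2.2 lists | the same without Week 8; last entry is Week 108/Final visit | 10 |
| SAP Table 2 | the 11 scheduled visits plus Final Observation | 12 |

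The lists differ from the protocol only by Week 8. They differ from Table 2 by Week 8 and by the merging of the last two rows.

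**3. Where an early stopper's value goes.** Take a Final Visit during Week 10, days (10 − 1) × 7 + 1 = 64 to 70. By the Table 2 windows it belongs to Week 8 (44 to 71). By the SAP 6.2 definition it is also that subject's Final Visit value, and so could enter the combined last row. The two readings place the same value in different rows.

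**4. Possible size of the mixing (assumed figures).** The documents state no discontinuation rate. Dosing 200 to have 177 evaluable implies a loss of 1 − 177/200 = 11.5%, or 23 subjects, by Week 48. That is an allowance for drop-out at the primary visit, not a treatment-discontinuation rate. If it is used as one, at a constant rate, the share stopped by Week 108 is p = 1 − (1 − d)^(108/48).

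If the combined row pools everyone, its mean falls below the completers' mean by p × (completer mean − early-stopper mean). For illustration, take completers at +12 and early stoppers at 0.

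| Assumed loss by Week 48 (d) | Share stopped by Week 108 (p) | Of 200 | Shortfall, p × 12 | Pooled mean |
|---|---|---|---|---|
| 5% | 10.9% | 22 | 1.3 | +10.7 |
| 11.5% | 24.0% | 48 | 2.9 | +9.1 |
| 20% | 39.5% | 79 | 4.7 | +7.3 |
| 30% | 55.2% | 110 | 6.6 | +5.4 |

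The +12 and 0 have no source in the documents, and the calculation assumes that every subject supplies a last value. At a data cut-off taken when the last subject reaches Week 48 (Protocol 8.1.3), the mix would be different again.

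**5. Window overlap.** Table 2 gives Week 96 as days 658 to 743 and Week 108 as 742 to 825, so days 742 and 743 belong to both. From Week 24 on, the other windows are 84 days wide (for example 154 to 237, and 742 to 825). Week 96 is 743 − 658 + 1 = 86.

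**The case against.** A reader might infer that Week 8 will go unreported and that one visit in eleven is lost for every scale. The documents do not support that. SAP 10.1.1 requires summaries and change from baseline at each assessment for all three instruments. SAP 10.2.2 promises mean and SD for each post-baseline visit, and 10.2.1 itself ends by asking for a confidence interval for each post-baseline comparison with baseline. Week 8 is collected, windowed and due to be summarised. What stands is that the two explicit lists disagree with this text.

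A reader might also infer that the last row certainly mixes two-year completers with early discontinuers. That is not established either. Table 2, which assigns data to visits by Rx day, keeps Week 108 and Final Observation apart. The combined label may only copy the Appendix D column that serves both visits, and footnote w there says that for subjects outside Extended Access the Week 108 visit is the final one. Pooling follows only if the label is read with SAP 6.2 and allowed to override Table 2. The SAP does not say that it does, but it does not exclude that reading.

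The two events also need not coincide. Protocol Appendix E places the Final Visit of Extended Access subjects at Week 216, after a separate Week 108 visit. That phase came in with the current amendment, whereas the SAP cites Amendments 1 and 2.

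**Conclusion.** The point holds as an internal inconsistency of low severity. The lists in SAP 10.2.1 and 10.2.2 omit a collected and windowed assessment that other parts of the plan require, and they combine two rows that Table 2 separates. Pooling in the last row is possible, not certain.

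The effect is confined to descriptive by-visit tables. These matter because the course of quality of life is what the trial studies, but the Week 48 primary estimate and the 177/200 sample size are untouched. The true size of any distortion in the last row cannot be stated. The illustrative shortfall of 1.3 to 6.6 points rests wholly on assumed discontinuation rates and assumed mean changes, and on the reading of the label under which values are pooled.

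**What to change.** 1. Add Week 8 to the visit lists in SAP 10.2.1 and 10.2.2.
2. Replace the combined last entry with two rows, as in Table 2: Week 108, assigned by its Rx-day window, and Final Observation, by the SAP 6.2 definition. Show the number of subjects in each.
3. Remove the overlap at days 742 and 743. Ending Week 96 at day 741 would give it the same 84-day width as its neighbours (658 + 83 = 741). Without this step, a separate Week 108 row would inherit the ambiguity.

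The cost is a short SAP wording change and two more rows per scale (10 to 12). It needs no new data, no new method and no change to the primary analysis.
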